3.8. Merging Strata

If treatment arms have less or equal to three subjects in one of the strata in ITT populations, the stratum cell will be combined to stratum “Other”. Based on enrollment, all strata with the exception of Leigh Syndrome will be combined in “Other”.

3.9. Visits During On-vatiquinone Period

The nominal visits during on-vatiquinone period will be reassigned for subjects randomized to placebo/vatiquinone treatment sequence as in [Table 2](#).

Table 2: Study Visits for On-vatiquinone Period

Study Visit	Nominal visit during on-vatiquinone period for treatment sequence vatiquinone/vatiquinone	Nominal visit during on-vatiquinone period for treatment sequence placebo/vatiquinone
Baseline	Baseline	

Study Visit	Nominal visit during on-vatiquinone period for treatment sequence vatiquinone/vatiquinone	Nominal visit during on-vatiquinone period for treatment sequence placebo/vatiquinone
Week 4	Week 4	
Week 8	Week 8	
Week 12	Week 12	
Week 24	Week 24	Baseline
Week 36	Week 36	Week 12
Week 48	Week 48	Week 24
Week 60	Week 60	Week 36
Week 72	Week 72	Week 48
Follow-up	Follow-up	Follow-up

3.10. Changes of Analysis from Protocol

There are no major changes in analysis from study protocol.

At the time of study design and enrollment, the initial plan of randomization and stratification was planned based on the disease subtype to include the following:

1. Alpers/DNA polymerase subunit gamma (POLG)
2. Leigh syndrome
3. Mitochondrial encephalomyopathy, lactic acidosis, and stroke-like episodes (MELAS) and
4. Other genetically confirmed mitochondrial disease secondary to mitochondrial mutation.

However, due to the challenges in identifying and enrolling participants who meet the inclusion and exclusion criteria for the study, there was a disparity in enrollment of subjects with the prespecified subtypes mentioned in the protocol (listed above). Only one subject was randomized for Alpers/(POLG) and no subjects were randomized for MELAS. Therefore, the only strata in the ITT population will be Leigh syndrome and “Other” (Section 3.8).

Considering the patient population currently enrolled into the study, we have pre-specified two specific mitochondrial disease subtypes, in addition to Leigh syndrome, that are of interest and in whom we seek to understand treatment effect independent of those recorded in the overall population. These additional disease subtypes are pontocerebellar hypoplasia type 6 (PCH6) secondary to arginine-tRNA synthetase 2 (RARS2) mutation and mt-aaRS2 disorders (for all mitochondrial aminoacyl tRNA synthetase disorders which includes subjects with RARS-2 mutations associated with PCH6 mutation). All analyses planned for the overall population will be repeated for Leigh syndrome, PCH6, and mt-aaRS2 disorders.

In the protocol, the secondary end point related to the change in motor seizures and total seizures was planned to be analyze in proportion of subjects with $\geq 25\%$, $\geq 50\%$, $\geq 75\%$, and 100% reduction. This proportion of change does not capture disease progression and potential increase in seizures. Therefore, the analysis groupings were changed to reflect the proportion of subjects with $>30\%$, 30% to -30% , $< -30\%$ to -60% , $> -60\%$ to -100% for motor seizure and total seizures will be summarized for double-blind period by treatment groups.

4. SUBJECT DATA

4.1. Participant Dispositions

The disposition of subjects in the double-blind period, including the number of subjects screened, the number of subject randomized, the number of randomized subjects who received at least 1 dose of study drug, and the number of subjects who prematurely discontinue study drug as well as the reason for the premature termination, number of subjects who complete the final follow up call and the reason the final call not completed will be tabulated for ITT population.

A similar table that includes number of subjects who received at least one dose of study drug, number of subjects who prematurely discontinue study drug as well as the reason for the premature termination, number of subjects who complete the final follow up call and the reason the final call was not completed will be produced for open-label extension period by treatment sequence for the ITT population.

Similar table will be tabulated for Safety population when ITT and Safety population are different.

4.2. Protocol Deviation

All protocol deviations will be summarized for the ITT population. A listing of all subjects with one or more important and non-important protocol deviations will be presented for the ITT population.

All-important protocol deviations will be identified and documented by PTC team prior to unblinding at soft lock.

4.3. Demographic and Baseline Characteristics

Demographics and baseline characteristics including age, sex, race, ethnicity, region, country, height, weight, body mass index (BMI), and disease subtype will be summarized by treatment for ITT Population.

4.4. Medical History

Medical history will be coded with the Medical Dictionary for Regulatory Activities (MedDRA, version 23.0, or later).

Medical history records will be summarized by treatment and by SOC and PT for ITT population.

A subject data listing of medical history will be provided.

4.5. Concomitant Medications and Non-Drug Treatments

All investigator terms for medications recorded on the case report form (CRF) will be coded using the World Health Organization (WHO) Drug Dictionary (Version MAR2020 or later).

Prior medications will be defined as medications started prior to the first dose of study drug. Concomitant medications will be defined as medications (other than the study drug) that (1) started before the first dose of study drug and were continuing at the time of the first dose of

study drug, or (2) started on or after the date of the first dose of study drug. Any medication started before the first dose of study drug and continued at the time of first dose will be considered as both prior and concomitant medications.

Any medication with partial or missing start date in which the prior medication status cannot be determined will be considered as a prior medication. Similarly, any medication with partial or missing end date in which the concomitant medication status cannot be determined will be considered as a concomitant medication.

Prior medication, concomitant medication during double-blind period, concomitant medication during on-vatiquinone period will be summarized as following for ITT population:

- Number and percentage of subjects with at least one prior/ concomitant medications.
- By Anatomical Therapeutic Chemical (ATC) level 2 and preferred term (PT).

A subject data listing of all prior and concomitant medications will be listed.

Prohibited medications will be identified prior to unblinding and will be listed separately.

4.6. Study Drug Compliance Based on Diary

Treatment compliance will be calculated as the percentage of the number of doses taken as recorded on diary out of what is expected to be taken in a period of interest,

$$\text{compliance} = \frac{\text{number of doses taken}}{3 \times \text{number of days in the period of interest (except on the day start first dose of OL period)}} \times 100\%$$

The number of days in the period of interest is defined as last dose date in the period of interest - first dose date in the period of interest + 1.

Last dose date during double-blind period is the same date as the start of the open-label period, and subject is expected to take 2 doses of the double-blind period medication and 1 dose of the open-label period medication. Denominator for the compliance calculation will be adjusted accordingly for subjects entered the open-label period.

The study drug compliance will be summarized by treatment for double-blind period, and by treatment sequence for open-label period, as well as for on-vatiquinone for Safety Population.

4.7. Seizure Diary Compliance Based on Diary

Seizure diary compliance is defined as the percentage of number of days with a valid seizure diary entry out of number of days during the period of interest.

$$\text{compliance} = \frac{\text{number of days with seizure diary}}{\text{number of days in the period of interest}} \times 100\%$$

The number of days in double-blind period is defined as last dose date in the double-blind period - first dose date in the double-blind period + 1. For subject who entered the open-label period, the duration for the double-blind period is defined as: last dose date in the double-blind period - first dose date in the double-blind period. The handling is because the last dose date during double-blind period is the same as during start of open-label period, and the seizure diary will

not record the time of the seizure, all the seizures that occur on that day will be considered as during open-label period.

The number of days in open-label period is defined as last dose date in the open-label period-first dose date in the open-label period+1.

The seizure diary compliance will be summarized by treatment for double-blind period for ITT population.

5. EFFICACY ANALYSIS

Efficacy analysis will be based on the ITT population, unless otherwise specified.

5.1. Primary Endpoint(s) Analysis

5.1.1. Definition of Endpoint(s)

The percent change in the motor seizure frequency per 28 days in the double-blind period in the ITT population will be the primary efficacy endpoint.

Motor seizure frequency will be counted across the entire 24 weeks (168 days) of the double-blind treatment period. Seizure frequency will be normalized to 28 days to allow for comparison of seizure frequency in the double-blind period to the seizure frequency observed during the 28-day run-in period. The 28-day run-in period will be used to establish the baseline seizure frequency.

During the study, subjects (and/or their parent/legal guardian) were required to record occurrence of seizures in a seizure diary on a daily basis. A blank entry in the seizure diary would be considered an invalid day; it is not considered to be an absence of seizures. Only days that have seizure diary information completed are considered to be valid entry days.

For calculation of the primary endpoint, the total number of motor seizures collected on valid entry days will be divided by the number of valid entry days and then multiplied by 28 to provide the average number of seizures normalized “per” 28 days. The formula to calculate this is shown below:

$$\text{Seizure frequency per 28 days during DB period} = \frac{\text{Total number of reported motor seizures during DB period}}{\text{Number of “valid” days with reported motor seizures during DB period}} \times 28$$

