3.5. Baseline

For safety endpoints, baseline for double-blind period and open-label period will be defined as the last measurement prior to or on the date of first dose date.

For efficacy endpoints during double-blind period, baseline is defined as the 28 days prior to randomization. Baseline definition for the seizure frequency, disease-related hospitalization days, and occurrence/recurrence of status epilepticus per 28 days will be calculated as the number of seizures, hospitalization days, and status epilepticus, respectively, during the run-in period, divided by the number of days in the run-in period, and multiplied by 28. Only “valid days” will be used in the calculation of seizure frequency per 28 days. A “valid day” is defined as a day where seizure counts information is present.

For summary, based on on-vatiquinone period, the baseline will be defined as the last measurement prior to the first dose of vatiquinone. ie, the last assessment prior to first dose in subjects with treatment sequence vatiquinone/vatiquinone, or the last assessment prior to first open-label vatiquinone in subjects with treatment sequence placebo/vatiquinone. For subjects who are randomized to placebo group in double-blind period and enter into the open-label period, all assessments conducted on the day they take last dose of double-blind period drug will be considered as baseline for the on-vatiquinone period.

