3.7. Missing Data Handling

In general, missing data will not be imputed, unless otherwise specified.

To minimize the impact from the missing data, the seizure frequency will be based on number of seizures on “valid days”. A “valid day” is defined as the day where seizure counts information is present.

In addition, a sensitivity analysis will be performed excluding all subjects with $< 80\%$ compliance in the seizure diary of valid days entered in the diary either during run-in period, or during double-blind period.

For analysis purposes, lab or PK values preceded by a “<” sign, ie, below the limits of quantification, will be considered as half of the limit of quantification. Lab or PK values preceded by a “>” sign, ie, above the limits of quantifications, will be considered as plus one unit of the minimum digit of the limit of quantifications. The original value will be included in the listing.

Per study design, last dose during double-blind period will be taken in the office the same day as first dose during open-label period, which will be taken at home later that day. When the dose time for first dose during open-label period is missing, all labs, vital signs taken on that day will be considered as prior to open-label period. All seizures, AE and concomitant medications that occurred on that day will be considered as occurred during the open-label period to be conservative, as all subjects will take vatiquinone during open-label period.

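### SAP 5.1.1 gives two incompatible denominators for the primary endpoint: all valid diary days in the prose, only valid days with motor seizures reported in the displayed formula

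*SAP*

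**What the plan says.** SAP 5.1.1 first settles what a usable diary day is. It states: "Only days that have seizure diary information completed are considered to be valid entry days". It adds: "A blank entry in the seizure diary would be considered an invalid day; it is not considered to be an absence of seizures". A completed entry of zero is therefore a valid day, and a blank is not.

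In the prose calculation that follows, the motor-seizure total "will be divided by the number of valid entry days and then multiplied by 28". The SAP then presents a formula as the way to compute this quantity, and labels its denominator as the number of valid "days with reported motor seizures during DB period".

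Elsewhere the rule matches the prose:
- **SAP 3.5 (Baseline):** the run-in count is "divided by the number of days in the run-in period, and multiplied by 28". The section then restricts seizure frequency to valid days, and a valid day "is defined as a day where seizure counts information is present".
- **SAP 3.7 (Missing Data Handling):** a valid day "is defined as the day where seizure counts information is present".
- **Protocol 8.4.2:** seizures times 28, divided by days in the interval, using valid days only, with the same definition of a valid day.

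None of these three places limits the denominator to days on which a seizure occurred.

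**The concern.** The two denominators are different quantities. Seizures per valid diary day is a frequency. Seizures per seizure-day measures how many seizures cluster on the days that have any. A treatment that works by producing more seizure-free days improves the first and may leave the second unchanged.

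The label sits on the endpoint that alone decides whether the study is declared positive and that gates both key secondary endpoints (SAP 3.6). Percent change in SAP 5.1.2 is computed from this frequency. The windowed analyses in 5.1.3, total seizures in 5.2.2.1 and the response categories in 5.2.2.2 also rest on seizure frequency. The sensitivity analyses in 5.1.3 change the subjects, the time window or the scale of change. None states a different denominator, so none would reliably expose a misprogrammed one. SAP version 2.0 added the endpoint detail in response to FDA comments, so this is text that ought to be unambiguous.

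**Working it through.** The plan gives no worked seizure frequency to reproduce. Its power figure (81% in the protocol, 80% in the SAP) reproduces at 80.6% to 82.0% by two Wilcoxon approximations and does not depend on this point.

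**Inputs from the documents.** Double-blind period of 168 days (SAP 5.1.1). Entry minimum of 6 motor seizures in the 28-day run-in (protocol 4.2). Percent change = 100 × (DB − BL)/BL (SAP 5.1.2).

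**Two rules.** Let T be total double-blind motor seizures, V valid diary days and S valid days with at least one motor seizure.
- Prose: 28 × T/V
- Display, read literally: 28 × T/S

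**A bound that needs no model.** Each seizure-day holds at least one seizure, so T/S ≥ 1 and the literal result is at least 28 whenever T > 0. If baseline follows SAP 3.5, a subject with a baseline below 28 could not show a reduction unless wholly seizure-free. In that case T = S = 0 and the result is 0/0, where the prose gives 0 and a change of −100%.

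**One subject at the entry minimum** (assumed: baseline 6, all 168 days valid, 18 seizures on 18 separate days).
- Prose: 28 × 18/168 = 3.0; (3.0 − 6)/6 = −50%
- Literal display: 28 × 18/18 = 28.0; (28.0 − 6)/6 = +367%

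**Range across baseline frequency** (assumed: Poisson daily counts, true halving, baseline as in SAP 3.5). With baseline b, the double-blind daily mean is λ = b/56, and the literal rate is 28λ/(1 − e^−λ). For b = 28, λ = 0.5, so the rate is 28 × 0.5/0.3935 = 35.6, a change of (35.6 − 28)/28 = +27%.

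| Baseline per 28 days | Prose | Literal display |
|---|---|---|
| 6 | −50% | +392% |
| 12 | −50% | +159% |
| 28 | −50% | +27% |
| 56 | −50% | −21% |
| 140 | −50% | −45.5% |
| 280 | −50% | −49.7% |

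**Trial level.** Illustrative simulations with 30 per arm and true reductions of about 10% and 50% disagree on power:
- Gamma-Poisson counts, rank ANCOVA, median baseline 40: medians of −8%/−49% (placebo/active) become +91%/+40%, and power goes from 89% to 80%. With median baseline 15, medians become +208%/+156% and power is about 77%.
- Poisson counts, rank-sum test, log-normal baseline with median about 30, log-scale between-subject SD of 0.5 in response: medians of −9%/−49% become +58%/+22%, and power goes from 97% to 33%.
- The second set-up with the literal label applied to baseline too: medians −2%/−20%, power 84%.

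**The case against.** The strongest reply is that the intent is not in doubt. The sentence introducing the display, SAP 3.5, SAP 3.7 and protocol 8.4.2 all point to every valid diary day, and the display claims only to show what that sentence says. The label can also be read loosely as days on which motor-seizure information was reported, zero included. The literal reading conflicts with the rest of the plan as well: a −100% change could never be computed, yet protocol 2.2.2 has a 100% reduction endpoint and SAP 5.2.2.2 has a category running to −100%.

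Most of this stands, and it settles which denominator is meant. It does not make the label correct. The numerator of the same fraction uses reported motor seizures to mean actual events, so consistent reading below the line gives seizure-days. SAP 4.7 shows that the SAP can name diary days plainly when it means them. A programmer working from the display would have a literal basis for the wrong denominator.

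A reader might also infer that the SAP defines baseline and double-blind frequency by different rules. It does not. SAP 3.5 restricts baseline seizure frequency to valid days, as the prose of 5.1.1 does for the double-blind period, and step (a) of SAP 5.1.2 derives both together. The asymmetry appears only if the literal label is used for the double-blind period alone.

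**Conclusion.** SAP 5.1.1 contradicts itself on the denominator of the primary endpoint, and the displayed formula is wrong as labelled. If it were programmed literally, the floor of 28 per 28 days and the 0/0 for seizure-free subjects would follow by arithmetic alone. A true halving could appear as a large increase in subjects with few seizures (+367% in the worked subject), while the error would be negligible at near-daily frequency (−49.7% against −50% at a baseline of 280). The figures between those ends rest on the assumed Poisson counts.

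A reader might infer that the primary result is wrong. The documents do not support that: they contain neither a result nor derivation code for this endpoint, and the surrounding text identifies the right denominator. Nor should any single power loss be quoted. The simulated falls run from 89% to 80% under one set of assumptions and from 97% to 33% under another. What remains is an inconsistent rule for the primary endpoint, with a risk of misprogramming that should be closed.

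**What to change.** Relabel the denominator in SAP 5.1.1: *Number of valid diary days during the DB period (days with a completed motor-seizure entry, including a recorded count of zero)*. Add one sentence stating that the same rule applies to the run-in baseline, the windowed analyses in 5.1.3 and, with total counts, the total-seizure analysis in 5.2.2.1. The last-12-week, last-4-week and total-seizure analyses already refer back to the primary analysis, so for them the sentence only makes the rule explicit. Confirm before soft lock that the derivation program uses this denominator, and include a test subject with recorded zero days and one with no double-blind seizures. The cost is the relabelled line, the added sentence and a code check. The endpoint, the model and the data collected do not change.

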5.1.2. Primary Analysis

For primary analysis, both the motor seizure frequencies per 28 days in the pre-randomization period as well as the percentage change in motor seizure frequencies per 28 days in the double-blind period will be rank transformed separately.

The analysis of covariance (ANCOVA) will then be conducted on this rank transformed data with treatment, and stratifying factor and the ranked pre-randomization phase seizure frequency per 28 days as a covariate. P-values will be computed between active and placebo treatment groups.

Due to an expected irregular distribution of seizure frequency, median will be the primary statistic of interest for the primary endpoint. The difference in median of the percent change from baseline between the two treatment groups will be estimated using Hodges-Lehmann estimator along with 95% CI for understanding the treatment effect size.

The stepwise approach to estimate the median difference of percent change using Hodges-Lehmann estimator is:

- a. derive the seizure frequency per 28 days for baseline (BL) and double-blind (DB) period.
- b. calculate the percent change from baseline as $100 \times (DB - BL)/BL$.
- c. apply the below SAS code of PROC NPAR1WAY nonparametric model to generate Hodges Lehmann Estimator:

```
*** Hodges Lehmann Estimator;  
proc npar1way data=<dataset name> HL ;  
  class <treatment variable name>;  
  var <percent change from baseline variable name>;  
  ods select HodgesLehmann;  
run;
```

5.1.3. Sensitivity Analysis for Primary Endpoint

The following sensitivity analyses are planned.

1. The similar analysis as described for the primary analysis will be repeated using the PP population.
2. An analysis using the same model as described for primary analysis excluding all subjects with <80% of valid days entered in the diary in run-in period and/or the double-blind period.
3. An analysis using the same model as described for primary analysis excluding all subjects who change anti-seizure medication or increase dose of anti-seizure medication not related to weight or begin/change in ketogenic diet during the study.
4. An analysis using the same model as described for primary analysis excluding all subjects who discontinued due to withdrawal, noncompliance, and death during the double-blind period.
5. Analysis as described in the primary analysis will be performed for percentage change from baseline in the motor seizure frequency per 28 days during the double-blind period completers ie, all subjects that took medication until the end of the double-blind period as specified by the protocol and have >80% compliance for seizure diary, for ITT analysis sets.
6. Change from baseline of number of motor seizure per 28 days in the double-blind phase will be performed using the same model as described for primary analysis.
7. Analysis as described in the primary analysis will be performed for percentage change from baseline in the motor seizure frequency per 28 days during the last 12 weeks in the double-blind phase for ITT.
8. Analysis as described in the primary analysis will be performed for percentage change from baseline in the motor seizure frequency per 28 days during the last 4 weeks in the

double-blind phase for ITT. The last 4 weeks is defined as start 141st day post randomization until last dose date during the double-blind phase.

9. Descriptive summary will be performed for percentage change from baseline in the motor seizure frequency per 28 days during the double-blind phase for ITT population excluding subjects that had coronavirus disease of 2019 (COVID-19) during the double-blind phase.
10. Descriptive summary will be performed for percentage change from baseline in the motor seizure frequency per 28 days during the double-blind phase for ITT population excluding subjects with a do not resuscitate (DNR) order.
11. The median and 95% CI of percent change from baseline in motor seizure frequency per 28 days will also be summarized for the ITT population during
 - Week 4 (day 1 – 28)
 - Week 8 (day 29 – 56)
 - Week 12 (day 57 – 84)
 - Week 16 (day 85 – 112)
 - Week 20 (day 113 – 140)
 - Week 24 (day 141 – 168)

